### 9.1 Clinical Assessments

All clinical assessments will be documented in the medical record, and this information will be abstracted from the medical record for analysis.

#### 9.1.1 Concomitant Medications

Concomitant medications such as antibiotics and analgesics will be documented at each clinical visit, and this information will be abstracted from the medical record.

### **9.1.2 Demographics**

Demographic information (age, parity, race, insurance status, and ethnicity) will be recorded as part of the initial visit and will be abstracted from the medical record. The site PI will supervise the data abstraction and replace the name with the Study ID prior to transferring the data to the UCSF research team. Demographic information will also be collected on the Day 3 Survey (see section 10.2).

### **9.1.3 Medical History**

At the initial visit, the following will be recorded in the medical record: date of service past medical history current medications blood pressure, weight, height, and medications prescribed or dispensed (Mifeprex® 200 mg, misoprostol 800 mcg, antibiotics, analgesics, other). At any follow-up visits, unusual symptoms such as heavy bleeding, excessive pain, or fever will be recorded, as well as any treatment given. Women will also be asked if they sought care elsewhere since the prior visit, and if so, what treatment, if any, they were given.

### **9.1.4 Physical Examination**

Blood pressure, weight, and height will be collected at the initial visit. A targeted physical examination will be performed at the clinic site according to their current practice. At some sites, gestational age of the pregnancy may be determined by patient history and physical examination.

### **9.1.5 Vital Signs**

Vital signs will be recorded at each clinical encounter.

### **9.1.6 Ultrasound**

Ultrasound may be performed at the initial visit to determine gestational age of the pregnancy (if it is not performed at the clinic site, the date and result of an outside ultrasound will be documented). Ultrasound may be performed at a follow-up visit to determine whether the abortion is complete or incomplete or if there is an ongoing pregnancy.

### **9.1.7 Other Clinical Procedures**

Patients may undergo uterine aspiration in case of heavy bleeding, incomplete abortion or ongoing viable pregnancy. This procedure will be detailed in the medical record.

### **9.1.8 Adverse Events**

We will track adverse events (AEs) as described in section 12.

## **9.2 Clinical Laboratory Measurements**

### **9.2.1 Pregnancy Test**

Women will be presenting for pregnancy termination, so pregnancy will be confirmed as part of the visit prior to recruitment, consent, and enrollment.

### **9.2.2 Hemoglobin**

If hemoglobin is measured, this result with the date of the test will be abstracted from the medical

record.

### **9.2.3 Serum human chorionic gonadotropin (hCG)**

Some patients will have serum hCG measured on the day of Mifeprex® prescription and again approximately 8 days after taking Mifeprex® to assess for completion of the abortion. These results with the date of the tests will be abstracted from the medical record.

### **9.2.4 Rhesus (Rh) factor**

Rh factor status will be determined for all patients. If the patient has a documented laboratory result of her Rh status, this will be added to her clinical record. If the patient does not have a documented laboratory result, a blood draw will be performed to assess Rh status. Patients who are found to be Rh-negative will be contacted to receive immunoglobulin (Rhlg) within 72 hours of taking mifepristone, either at the clinic site, or arrangements will be made to administer it at a nearby clinic or hospital.

## **10 PATIENT ACTIVITIES BY DAY**

### **10.1 Day 0**

This is the day the patient participant is enrolled in the study. Patients who indicate they are interested in medication abortion will be informed about the study by their treating clinician. If they are interested in participating in the study, they will undergo standard assessment, including an assessment for gestational age, which will include either an ultrasound or physical examination, and counseling for medication abortion. They will also be informed about the study activities and asked to consent for participation. Once eligible participants have signed the Danco Patient Agreement and any other specific consent forms for the site, they will be asked to complete a contact information sheet, which includes their contact information and preferences. Patients may be enrolled during the initial visit if they are eligible based on the information available at the time. It is possible that at this point ultrasound results may still be pending (for example if the patient needed to be referred elsewhere for an ultrasound); if this is the case, patients will be tentatively enrolled in the study (asked to complete the informed consent process and the contact form) and informed that their participation is contingent on confirmation of their gestational age. Once the ultrasound results are known, the provider will update the eligibility form. After determining that a patient is eligible for the study, a clinician at the site will then transmit a prescription for Mifeprex® 200 mg, misoprostol 800 mcg, and any other necessary medications (such as 800 mg ibuprofen) to the mail-order pharmacy, and the patient will be given information about when and how to take the medications. The patient will be informed that the pharmacy will contact them by phone to confirm their mailing address, drug allergies, and whether they have additional questions (note: the patient may also call the pharmacy directly). The patient will be informed to expect the delivery of medications as soon as the following business day and no later than 3 business days later.

### **10.2 Day 3 Survey**

On Day 3 (after the prescription is sent), patient participants will be sent by email or text message, depending on their preference, a link to an online survey about their experience receiving the medications, as well as to collect sociodemographic information (see Day 3 survey). If a participant prefers, or if she does not respond to the email link, she may be contacted by telephone to complete the survey over the phone or sent reminders by text message. The survey will focus on her experience receiving the medications by mail, including whether and when she received the medications and the quality of the packaging, as well as her experience taking the Mifeprex®. We will also collect

information about if and when the Mifeprex® and misoprostol might have been diverted to another person. If they do not respond to the survey within two days, participants will be contacted by telephone or text message up to three times. If a participant has decided not to proceed with medication abortion (for any reason), she will be encouraged to complete the Day 3 survey, where this information will be captured. If a woman obtained the Mifeprex® and/or misoprostol and has decided not to take the medication(s), she will be asked to return them to the clinic.

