### 2.1 Risk / Benefit Assessment

Potential medical risks to medication abortion patients participating in the study are the same as those they would incur by undergoing a medication abortion outside of the study. Because they are undergoing the same clinical assessment prior to obtaining MA, there is no reason to believe that dispensing of Mifeprex® by pharmacists will increase the risks of the procedure. In addition, patients will be given detailed information about warning signs, such as heavy bleeding, that should prompt them to seek care.

The main risk related to the study is that the patient may not take Mifepristone® at the time they are told to—and potentially that they may take it later than 70 days' gestation (the current FDA gestational age limit). There is also a risk that they may give the medication to someone else. It should be noted that these risks exist currently since the Mifepristone® label allows them to take the medication at home, and there is no reason to believe that the risks will increase due to the study. Patients will also be surveyed on Day 3 to be certain they received and took the Mifepristone® as instructed. The eligibility criteria for this study will limit gestational age of participants to 63 days at the time of prescribing, so as to minimize the risk of patients taking the medications after 70 days due to delays in receiving the drugs. Women who do not return for follow-up at the clinic will be contacted by phone or email to obtain information about abortion completion and adverse events. Other potential risks include any social risks involved if information they reveal about their seeking an abortion or other sensitive issues were to be disclosed outside of the research.

There are minimal risks to providers for participating in the study. The participating clinics will not be identified in any publications. There is a potential risk that participating clinics will experience anti-abortion picketers if participation in the study becomes known, and this has been discussed with the management of each clinic.

These data will be used to assess whether it is feasible for ob/gyn and primary care clinics to provide medication abortion and for patients to receive the medications by mail, which could help to improve access to early abortion.

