## 8.5 Study Drug Accountability

An accurate and current accounting of the dispensing and return of study drug for each subject will be maintained on an ongoing basis by a member of the study site staff based on the records maintained by the mail-order pharmacy and the clinics. The number of study drugs transferred to the mail-order pharmacy, dispensed, and returned by the subject, will be recorded on the Investigational Drug Accountability Log. The study PI will verify these documents throughout the course of the study.

Participants who receive mifepristone by mail as part of the study but subsequently indicate that they do not plan to take the medications will be encouraged by the study team to return the medications to the clinic site. The clinic site will document that the medications were returned and then either safely dispose of the medications, deliver the medications to a pharmacy where safe disposal is possible, or mail the medications to the UCSF study team and the UCSF study team will take the medications to a

safe disposal site. If the participant does not want to go to the clinic site, the study team will send the participant a postage-paid mailer to ship the unused medications to the UCSF study team, who will then safely dispose of them.

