## 8.6 Measures of Treatment Compliance

Participant patients will be contacted on Day 3 and Day 14 after the prescription is sent to complete online surveys, which are detailed below in section 10.2. As part of these surveys, patients will be asked if and when they took the Mifepristone® and if and when they took misoprostol. If they have not yet taken the Mifepristone®, they will be asked when they plan to take it, and they will be contacted after that date to complete the Day 3 Survey. If they received the Mifepristone® but decided not to take it, they will be asked whether they returned it to the study clinic as instructed.

The research team will review all participant survey responses upon submission to ensure treatment compliance. If a participant reports being seen somewhere else for a complication or reports any unusual symptoms in either survey, the research team will inform the site PI and encourage the patient to contact the clinic. In addition, the research team will receive automatic notifications through the online survey platform, Qualtrics, in the following cases, after which the team will contact the participant by email and/or telephone to follow up:

- If a participant reports taking the misoprostol vaginally (instead of buccally)
- If a participant reports not taking the misoprostol after taking mifepristone
- If a participant reports taking mifepristone at >70 days gestation (based on the gestational age dating at initial clinic visit)
- If a participant reports taking the misoprostol <24 hours or >48 hours after the mifepristone
- If a participant reports taking the misoprostol but not taking the mifepristone

This information will enable the research team to monitor and capture all episodes of incorrect administration of mifepristone and/or misoprostol.

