## 12 ADVERSE EXPERIENCE REPORTING AND DOCUMENTATION

### 12.1 Adverse Events

Adverse Events (AEs) are to be reported only for untoward medical events that occur in participants after they have enrolled in the study. Only new untoward events, or a worsening of an existing condition, are considered AEs. Conditions that were present before enrollment into the study, and that remain stable or improve during the study, are not considered AEs. Only serious or unexpected AEs that are possibly, probably, or definitely related to the research will be submitted to the UCSF IRB. Diversion of Mifeprex® obtained in the study to someone other than the participant will also be considered an AE.

Information regarding AEs or SAEs may be first obtained by the clinical or study staff, as both will communicate with the participant at her visits and by phone.

Details about each AE or SAE will be recorded on an AE/SAE Form. This form will require the following information to be collected: diagnosis, onset date, resolution date, source of information, severity, treatment given, relationship to the study, action taken, and comments.

The physician site PI will have safety oversight of participants at the site, will assess AEs and SAEs, and will report them to the study PI and research team, who will then report to the UCSF IRB as

needed. The site PI, in consultation with the study PI, will determine the relationship of the AE to study treatment as definitely related, probably related, possibly related, or unrelated; and the severity of the AE as mild, moderate or severe. For AEs or SAEs that have not resolved at the time of learning of the event, the study team and the site PI will monitor the event until the event is resolved or has stabilized.

The study PI is also responsible for reporting all AEs to all relevant Institutional Review Boards (IRBs). All AEs that are related to the study and are serious or affect IRB approval will be reported by the PI to the relevant IRBs according to IRB requirements. UCSF requires that an internal (on-site) AE that the PI determines to be related to the study and serious or unexpected shall be reported within 5 working days of the UCSF PI's knowledge. External (off-site) AE's that change the study risks/benefits or requires a UCSF IRB modification must be reported within 10 working days of the UCSF PI's knowledge. Diversion of Mifeprex® will be reported to the FDA within 15 days of the UCSF PI's knowledge.

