We are unable to similarly assess whether the prevalence of clinically significant adverse events differs between the mail-order dispensing model and historical controls given the very low frequency of this outcome (<0.5%) (Upadhyay, Desai et al. 2015). A sample size of over 10,000 is required to power such an analysis and is not feasible in the proposed study. Thus, our analysis of safety outcomes will be exploratory. Using a patient survey and medical record review, we will thoroughly document women's experiences with any adverse events. In particular we will be interested in documenting adverse events that could be related to mail-order dispensing. For example, if the delivery of the medication was delayed, which caused a patient to undergo medication abortion after 70 days gestation and she had heavy bleeding requiring an emergency department visit, we would consider this to be possibly related to the mail-order dispensing model. Additional safety outcomes include the proportion of participants who take mifepristone after 70 days gestation and the proportion that divert the medication to someone else.

Provider acceptability, including clinician and staff perspectives on the timing and logistics, quality of care, clinic flow, cost, and sustainability of the mail-order dispensing of mifepristone and misoprostol, will be explored through qualitative analysis of in-depth open-ended interviews. We will invite all clinicians and staff who were involved in identifying and recruiting patients, communicating with the mail-order pharmacy, and/or following up with patients about their clinical care in the study, to participate in an interview at the end of the study period.

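### Diversion, a stated safety outcome, rests essentially on participant report and is never reconciled with the plan's own dispensing, return, intake and outcome records

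*Combined protocol and SAP*

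**What the plan says.** Diversion appears in three roles. Section 2.1 names it as a risk: "There is also a risk that they may give the medication to someone else". Section 16.4 makes it a safety outcome: "the proportion that divert the medication to someone else". Section 12.1 states that "Diversion of Mifeprex® obtained in the study to someone other than the participant will also be considered an AE", with a report to the FDA within 15 days of the study PI learning of it.

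Two routes bring a diversion to light. Section 10.2 has the Day 3 survey collect "information about if and when the Mifeprex® and misoprostol might have been diverted to another person". Section 12.1 adds that "Information regarding AEs or SAEs may be first obtained by the clinical or study staff", and explains this by staff contact with the participant at visits and by phone.

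Other records bear on the fate of each pack:

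- Section 8.5: an "accounting of the dispensing and return of study drug for each subject will be maintained on an ongoing basis". Numbers "dispensed, and returned by the subject, will be recorded on the Investigational Drug Accountability Log". Intake is not among the items listed for the log.
- Section 8.6: in the Day 3 and Day 14 surveys "patients will be asked if and when they took the Mifepristone® and if and when they took misoprostol". Those who received Mifeprex but decided against it are asked whether they returned it.
- Section 10.5: abortion outcome is abstracted from the chart, with a review 6 weeks after enrolment.

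No section joins these records to classify packs. Section 16.4 gives no data source, denominator or missing-data rule for the diversion proportion. Its population for effectiveness and safety endpoints is enrolled patients who took at least one of the two drugs and have follow-up data.

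**The concern.** A participant who passed on a restricted drug has a reason not to say so, and one who cannot be reached cannot say so. Both push a self-reported count toward zero. A pack that arrived, was not taken and did not come back, or whose recipient was lost, leaves no trace in the result unless someone volunteers the fact. The five automatic alerts in section 8.6 concern incorrect administration; none is triggered by a pack received, not taken and not returned.

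The population adds a second gap. A participant who gave away both drugs took neither, so the section 16.4 safety population would exclude precisely the event being counted. Section 13.3 also replaces participants who withdraw before taking the drugs, although a pack may already have been mailed to them.

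The study is intended to inform possible changes to the dispensing restriction (section 2). A reported diversion of zero would be read as evidence on that question, with nothing beside it to show how many packs could not be traced.

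**Working it through.** **Inputs.** Recruitment of 440 to 625 in the main study, 10% loss to follow-up, and about 400 to 560 analysed (sections 16.3 and 16.6). The plan states no expected rate, precision target or threshold for diversion.

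**1. The plan's own figure.** 440 × (1 − 0.10) = 396, stated as about 400. 625 × 0.90 = 562.5, stated as about 560. Both reproduce.

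**2. Self-report alone.** If nobody reports diversion, the exact two-sided 95% upper limit is 1 − 0.025^(1/n):

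- n = 400: 0.92%
- n = 560: 0.66%

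**3. The log alone.** Dispensed minus returned treats every pack that was swallowed as possibly diverted. Assume 0 to 5% of followed-up patients do not take the drug and half or all of those packs come back. Then 95% to 100% of packs remain open. For example, with no loss, 5% untaken and all returned: (440 − 22)/440 = 95%. The log by itself tells us nothing useful.

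**4. Log linked by subject to intake.** Unaccounted = dispensed − undelivered − returned − taken. Set undelivered to 0 and assume that the loss rate applies to packs dispensed and that lost patients have no intake record.

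| Assumed loss | Untaken packs among followed-up patients | Of 440 | Of 625 |
|---|---|---|---|
| 5% | all returned | 22 (5.0%) | 31 (5.0%) |
| 10% (plan) | all returned | 44 (10.0%) | 62.5 (10.0%) |
| 10% (plan) | 5% untaken, half returned | 53.9 (12.3%) | 76.6 (12.2%) |
| 15% | all returned | 66 (15.0%) | 94 (15.0%) |
| 15% | 5% untaken, half returned | 75.3 (17.1%) | 107 (17.1%) |

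The third row for 440: followed up 396; untaken 396 × 0.05 = 19.8; returned 9.9; taken 376.2; unaccounted 440 − 9.9 − 376.2 = 53.9.

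**5. Comparing steps 2 and 4.** At 10% loss the unaccounted share is 10/0.92 = 10.9 to 10/0.66 = 15.2 times the zero-event limit. These are different quantities: the limit reflects sampling error among responders, and the share reflects missing information. The comparison shows only that the missing information dominates.

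**6. What step 4 still misses.** A participant who diverts the drug but reports taking it is subtracted as taken. The linked figure thus errs in both directions: too high where non-responders took the drug, too low where intake is falsely reported.

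**The case against.** The strongest reply is that diversion does not hang on one survey item. It is an adverse event assessed by the site PI. Intake and return are asked about, the team reviews every survey on submission, sites document physical returns, and charts are reviewed. This stands in part: a reader might infer that a single question is the only measure, and the documents do not support that. Detection still depends mainly on what the participant says, however, and the records are never brought together.

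Three other strong readings also fail:

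- **The log would bound diversion.** It records dispensing and return, not intake (step 3). Even when linked, the result is no upper bound (step 6).
- **Untraced packs are counted as not diverted.** No rule says so. Section 16.4 restricts its population to those with follow-up and declines to assume success where follow-up is missing, so untraced packs would more naturally drop out than count as non-events.
- **The plan will publish a misleadingly narrow interval.** No interval for diversion is planned; the limits in step 2 are illustrative.

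It can also be said that section 16.4 calls the safety analysis exploratory, that section 2.1 notes this risk already exists with home use, and that section 16 defers detail to a later SAP. All true; they limit the weight of the point and make it easy to repair. Finally, section 16.1 defines its analysis set as eligible patients who receive the dose. That might be read as covering everyone who was mailed a pack, but it conflicts with the narrower population in section 16.4, and nothing says which governs diversion.

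**Conclusion.** The point holds as a gap in ascertainment and reporting. Diversion is ascertained essentially through participant report, packs of unknown fate are left out of the result, and the section 16.4 safety population, if applied, would remove participants who gave away both drugs or have no follow-up.

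The size is illustrative: about 10% of packs untraced at the plan's loss allowance, 5% to 15% if loss is 5% to 15%, and up to about 17% if some untaken packs are not returned. This carries a power-calculation allowance over to packs dispensed. Section 8.1 defines loss as no completed follow-up surveys and no clinic contact. If the 10% follows that definition, charts will resolve few of these packs; if it means survey non-response only, charts could resolve an unknown share. The bias from deliberate concealment cannot be quantified from the documents.

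No sample-size or power figure is wrong on this account, since none concerns diversion.

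**What to change.** In section 16.4, or the SAP still to be written:

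1. State that the denominator for diversion is all Mifeprex packs dispensed, including those sent to participants who withdrew, were replaced or were lost.
2. Beside self-reported diversion, give the number and proportion of unaccounted-for packs: dispensed, minus undelivered, minus logged as returned, minus taken.
3. Within taken, show intake supported by the clinical record separately from intake by self-report only.
4. Label the line as unaccounted-for packs, not as an upper bound on diversion. Add a note that it overstates diversion where non-responders took the drug and misses diversion hidden by a false report of intake.

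The cost is a short SAP paragraph and one table, linking by study ID the dispensing, return, survey and chart data that the plan already collects. No new patient contact is needed and clinical care does not change. The downside is that an untraced share near 10% could be misread as a diversion rate, which the label and note are there to prevent.
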